8.4 Pharmacokinetic Data Handling

8.4.1 Lower Limit of Quantification of lenvatinib Plasma Concentration and Nivolumab Serum Concentration

The LLOQ of lenvatinib plasma concentrations is 0.100 ng/mL

The LLOQ of nivolumab serum concentrations is 0.200 µg/mL

8.4.2 BLQ Handling for Calculation of PK Parameters

While calculating PK parameters in WinNonlin, BLQ values will be handled according to 302-104.01-MNL, for non-compartmental pharmacokinetic analysis.

8.4.3 BLQ Handling for Developing Concentration-Time Profiles

When developing individual concentration-time profiles, BLQ values will be handled according to 302-104.01-MNL for non-compartmental pharmacokinetic analysis.

8.4.4 Handling of Anomalous Concentration Values

The handling of anomalous concentration values will follow the guidance in the SWP for non-compartmental pharmacokinetic analysis (302-104.01-MNL).

8.4.5 General Rules for Presentation of Drug Concentrations and PK Parameters

When presenting individual/raw (raw, hereafter) values and summary statistics, the following rule will be applied: for drug concentrations and concentration-dependent pharmacokinetic parameters, all summary statistics (mean, median, geometric mean, SD and coefficient variation (CV)) will have 3 significant digits. For t_{max} and $t_{ss,max}$, raw values and their median are shown in fixed 2 decimal places.

Variable	Unit	N	Digit rule	Raw/	Mean	SD	Geometric	CV (%)
				Minimum/ Maximum	Median		Mean	
drug concentration	ng/mL	X	Significant digits	3	3	3	-	-
C_{max} , $C_{ss,max}$, C_{min} , $C_{ss,av}$	ng/mL	X	Significant digits	3	3	3	3	3
t_{max} , $t_{ss,max}$	h	X	Fixed decimal places	2	2	-	-	-
$\lambda_z(C1D1\&D15)$	1/h	X	Significant digits	3 (Listing only)	-	-	-	-
$t_{1/2}(C1D1\&D15)$	h	X	Significant digits		3	3	3	3
$AUC_{(0-t)}$, $AUC_{(0-inf)}$, $AUC_{(0-t)}$, $AUC_{(0-r)}$	ng·h/mL	X	Significant digits	3	3	3	3	3
CL/F , CL_{ss}/F	L/h	X	Significant digits	3	3	3	3	3
$V_z/F(C1D1\&D15)$	L	X	Significant digits	3	3	3	3	3
R_{ac}		X	Significant digits	3	3	3	3	3
PTF ratio	%	X	Significant digits	3	3	3	3	3

Mean, SD, geometric mean and CV will not be calculated for t_{max} , $t_{ss,max}$.

CV(%)= $\sqrt{\exp[SD^2/2] \text{ of log transformed data}} - 1 \times 100$

NOTE

1. The following parameters are reported in the CSR, but appear in Listings only. They are important information to confirm that individual $t_{1/2}$ and its related parameters such as $AUC_{(0-inf)}$ are appropriately derived and allow those PK parameters to be reproduced when necessary.
 - a. Time points used for estimation of λ_z (lower and upper)
 - b. Number of the time points used for λ_z
 - c. Adjusted regression coefficient (R_{2adj})
 - d. Percentage of $AUC_{(0-inf)}$ obtained by extrapolation (% AUC_{ex})
 - e. The last time points used for calculation of $AUC_{(0-t)}$ (t_{last})

In Listings, a) and e) are shown in same digits as actual sampling time after dosing used for calculation of PK parameters. For b), integer number is used in Listings. For c) and d), significant 3 digits are used in Listing.

8.4.6 Handling of Individual Data

The following cases will be excluded for the calculation of summary statistics.

- Blood samples at predose are collected after administration
- Overdose
- Blood samples for nivolumab PK assessment are collected when the most recent dosing of nivolumab is interrupted.
- Blood samples for lenvatinib PK assessment are collected when the most recent dosing of lenvatinib is reduced or interrupted.
- Regarding lenvatinib PK assessment from Cycle 1 Day 1 to Cycle 1 Day 16 in Part 1, blood samples for lenvatinib PK assessment are collected after dose reduction or interruption of lenvatinib by Cycle 1 Day 15.
- Dosing and/or sampling date/time are missing
- Blood samples are not taken in the nominal time point
- Concentration data collected at Discontinuation or Off-Treatment visit.

The following case will be determined individually.

- Significant deviation from the allowance of PK blood sampling schedule. However, concentration data at predose will not be excluded when the blood sampling is collected at predose on the scheduled day.
- There is discrepancy between planned and actual volume of nivolumab dosing.
- Concentration data is not scientifically valid (e.g, concentration at predose on Cycle 1 Day 1 is not BLQ and concentration at just completion of dosing is BLQ.)

9 PROGRAMMING SPECIFICATIONS

The rules for programming derivations and dataset specifications are provided in separate documents.

10 STATISTICAL SOFTWARE

All statistical analyses will be conducted by Takumi Information Technology, using validated standard programs or double programming. For analyses needed in data review, single programming will be used.

All statistical analyses will be performed using SAS (version 9.3 or later). As necessary, other validated statistical software will also be used.

11 MOCK TABLES, LISTINGS, AND GRAPHS

The study TLG shells will be provided in a separate document, which will show the content and format of all tables, listings, and graphs in detail.

13 APPENDICES

13.1 National Institute for Health: Common Terminology Criteria for Adverse Events (CTCAE) Version 4.03

National Cancer Institute (NCI) Cancer therapy evaluation program Common Terminology Criteria for Adverse Events (CTCAE) version 4.0 May 2009 (v4.03 June 2010) is available online at:

http://evs.nci.nih.gov/ftp1/CTCAE/CTCAE_4.03_2010-06-14_QuickReference_5x7.pdf

CTCAE grades for selected laboratory parameters are listed in the table below, where ULN is the upper limit of normal and LLN is the lower limit of normal.

Lab Parameter	NCI Common Terminology Criteria for Adverse Events (CTCAE) - SI Units				
	Grade 1	Grade 2	Grade 3	Grade 4	Grade 5
Hematology					
Hemoglobin (low)	100 - <LLN (g/L)	80 - <100 (g/L)	<80 (g/L)	—	Death
Hemoglobin (high)	Increase in >0 - 20 g/L above ULN (ie., Increase in >0 - 2 gm/dL above ULN) or above baseline if baseline is above ULN	Increase in >20 - 40 g/L above ULN (ie., Increase in >2 - 4 gm/dL above ULN) or above baseline if baseline is above ULN	Increase in >40 g/L above ULN (ie., Increase in >4 gm/dL above ULN) or above baseline if baseline is above ULN	—	—
Platelet Count (PLT) (low)	75 - <LLN ($\times 10^9/L$)	50 - <75 ($\times 10^9/L$)	25 - <50 ($\times 10^9/L$)	<25 ($\times 10^9/L$)	—
White Blood Cell Count (WBC) (low)	3 - <LLN ($\times 10^9/L$)	2 - <3 ($\times 10^9/L$)	1 - <2 ($\times 10^9/L$)	<1 ($\times 10^9/L$)	—
White Blood Cell Count (WBC) (high)	—	—	>100 $\times 10^9/L$ (ie., >100,000/mm ³)	—	Death
Lymphocytes (low)	0.8 - <LLN ($\times 10^9/L$)	0.5 - <0.8 ($\times 10^9/L$)	0.2 - <0.5 ($\times 10^9/L$)	<0.2 ($\times 10^9/L$)	—
Lymphocytes (high)	—	>4 - 20 ($\times 10^9/L$) (ie., >4,000 - 20,000/mm ³)	>20 ($\times 10^9/L$) (ie., >20,000/mm ³)	—	—
Neutrophils (low)	1.5 - <LLN ($\times 10^9/L$)	1 - <1.5 ($\times 10^9/L$)	0.5 - <1 ($\times 10^9/L$)	<0.5 ($\times 10^9/L$)	—

Lab Parameter	NCI Common Terminology Criteria for Adverse Events (CTCAE) - SI Units				
	Grade 1	Grade 2	Grade 3	Grade 4	Grade 5
Blood Coagulation					
INR (high)	>1 - 1.5 x ULN	>1.5 - 2.5 x ULN	>2.5 x ULN	—	—
Blood Chemistry					
Albumin (low)	30 - <LLN (g/L)	20 - <30 (g/L)	<20 (g/L)	—	Death
Alkaline Phosphatase (ALP) (high)	>ULN - 2.5 x ULN	>2.5 - 5.0 x ULN	>5.0 - 20.0 x ULN	>20.0 x ULN	—
ALT (SGPT) (high)	>ULN - 3 x ULN	>3 - 5.0 x ULN	>5.0 - 20.0 x ULN	>20.0 x ULN	—
AST (SGOT) (high)	>ULN - 3 x ULN	>3 - 5.0 x ULN	>5.0 - 20.0 x ULN	>20.0 x ULN	—
Total Bilirubin (high)	>ULN - 1.5 x ULN	>1.5 - 3.0 x ULN	>3.0 - 10.0 x ULN	>10.0 x ULN	—
Calcium, serum-low (hypocalcemia)	2.0 - <LLN (mmol/L) (ie., 8.0 mg/dL - <LLN) *	1.75 - <2 (mmol/L) (ie., 7.0 - <8.0 mg/dL) *	1.5 - <1.75 (mmol/L) (ie., 6.0 - <7.0 mg/dL) *	<1.5 (mmol/L) (ie., <6.0 mg/dL) *	Death
Calcium, serum-high (hypercalcemia)	>ULN - 2.9 (mmol/L) (ie., >ULN - 11.5 mg/dL) *	>2.9 - 3.1 (mmol/L) (ie., >11.5 - 12.5 mg/dL) *	>3.1 - 3.4 (mmol/L) (ie., >12.5 - 13.5 mg/dL) *	>3.4 (mmol/L) (ie., >13.5 mg/dL) *	Death
Cholesterol (high)	>ULN - 7.75 mmol/L	>7.75 - 10.34 mmol/L	>10.34 - 12.92 mmol/L	>12.92 mmol/L	—
CPK (high)	>ULN - 2.5 x ULN	>2.5 x ULN - 5 x ULN	>5 x ULN - 10 x ULN	>10 x ULN	—
Creatinine (high)	>1 - 1.5 x baseline; >ULN - 1.5 x ULN	>1.5 - 3.0 x baseline; >1.5 - 3.0 x ULN	>3.0 x baseline; >3.0 - 6.0 x ULN	>6.0 x ULN	—
GGT (gamma-glutamyltransferase) (high)	>ULN - 2.5 x ULN	>2.5 x ULN - 5.0 x ULN	>5.0 x ULN - 20.0 x ULN	>20.0 x ULN	—
Glucose, serum-low (hypoglycemia)	3 - <LLN (mmol/L)	2.2 - <3 (mmol/L)	1.7 - <2.2 (mmol/L)	<1.7 (mmol/L)	Death

Lab Parameter	NCI Common Terminology Criteria for Adverse Events (CTCAE) - SI Units				
	Grade 1	Grade 2	Grade 3	Grade 4	Grade 5
Glucose, serum-high (hyperglycemia)	ULN – 8.9 (mmol/L)	>8.9 – 13.9 (mmol/L)	>13.9 – 27.8 (mmol/L)	>27.8 (mmol/L)	Death
Lipase (high)	>ULN – 1.5 x ULN	>1.5 – 2.0 x ULN	>2.0 – 5.0 x ULN	>5.0 x ULN	—
Magnesium (low)	<LLN – 0.5 (mmol/L)	<0.5 – 0.4 (mmol/L)	<0.4 – 0.3 (mmol/L)	<0.3 (mmol/L)	Death
Magnesium (high)	>ULN – 1.23 (mmol/L)	—	>1.23 – 3.30 (mmol/L)	>3.30 (mmol/L)	Death
Triglyceride (hypertriglyceridemia) (high)	1.71 – 3.42 (mmol/L)	>3.42 – 5.7 (mmol/L)	>5.7 – 11.4 (mmol/L)	>11.4 (mmol/L)	Death
Phosphate, serum-low (hypophosphatemia)	0.8 - <LLN (mmol/L)	0.6 - <0.8 (mmol/L)	0.3 - <0.6 (mmol/L)	<0.3 (mmol/L)	Death
Potassium, serum-low (hypokalemia)	3.0 - <LLN (mmol/L)	—	2.5 - <3.0 (mmol/L)	<2.5 (mmol/L)	Death
Potassium, serum-high (hyperkalemia)	>ULN – 5.5 (mmol/L)	>5.5 – 6.0 (mmol/L)	>6.0 – 7.0 (mmol/L)	>7.0 (mmol/L)	Death
Uric Acid (hyperuricemia) (high)	>ULN – 590 (umol/L)	—	—	>590 (umol/L)	—
Sodium, serum-low (hyponatremia)	130 - <LLN (mmol/L)	—	120 - <130 (mmol/L)	<120 (mmol/L)	Death
Sodium, serum-high (hypernatremia)	>ULN - 150 (mmol/L)	>150 - 155 (mmol/L)	>155 - 160 (mmol/L)	>160 (mmol/L)	Death
Urinalysis					

[figure not shown]
Lab Parameter	NCI Common Terminology Criteria for Adverse Events (CTCAE) - SI Units				
	Grade 1	Grade 2	Grade 3	Grade 4	Grade 5

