9.5.1.5.3 LABORATORY MEASUREMENTS

Clinical laboratory tests to be performed, including hematology, chemistry, and urinalysis, are summarized in Table 8. The Schedule of Procedures/Assessments (Table 9) shows the visits and time points at which blood for clinical laboratory tests and urine for urinalysis will be collected in the study. Clinical laboratory tests will be performed at each site.

Table 8 Clinical Laboratory Tests

Category	Parameters
Hematology	RBC count, hemoglobin, hematocrit, platelets, and WBC count with differential (basophils, eosinophils, lymphocytes, monocytes, neutrophils)
Anticoagulant test	INR ^a
Chemistry	
Liver function tests	Alkaline phosphatase, aspartate aminotransferase, alanine aminotransferase, gamma glutamyl transpeptidase, total bilirubin, direct bilirubin
Renal function tests	Blood urea nitrogen, creatinine
Other	Glucose, albumin, total cholesterol, triglycerides, phosphorus, lactate dehydrogenase, total protein, sodium, potassium, chloride, calcium, magnesium, ammonia ^b , amylase ^c , lipase ^c , ACTH ^e , cortisol ^e
Tumor marker	AFP
Thyroid function tests	TSH, FT4
Virus tests ^b	HIV antibody, HCV antibody, HBs antigen, HBs antibody, HBc antibody, HBV DNA, HCV RNA, HDV antibody or HDV RNA ^d
Urinalysis	pH, protein, glucose, ketones, RBCs, specific gravity

AFP = α -fetoprotein, INR = International Normalized Ratio

a: INR will be assessed on C2D1 and every cycle thereafter.

b: Screening only. Data within 28 days before the first dose can be used.

c: Amylase and lipase will be measured at Screening, C2D1 and every cycle thereafter.

d: Subjects with hepatitis B only

e: If necessary, appropriate laboratory tests such as adrenal cortical function test (ACTH, cortisol) to be added.

A laboratory abnormality may meet the criteria to qualify as an AE as described in this protocol (see Section 9.5.1.5.1). In these instances, the AE corresponding to the laboratory abnormality will be recorded on the CRF. If AEs were assessed during unscheduled visits, all the data corresponding to the laboratory abnormality will also be recorded on the CRF.

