9.5.2 Schedule of Procedures/Assessments

9.5.2.1 Schedule of Procedures/Assessments

Table 9 presents the schedule of procedures/assessments for the study.

Table 9 Schedule of Procedures/Assessments in Study E7080-J081-117 (for Part 1 and Part 2)

Phase	Pretreatment		Treatment								Follow-up	
Period	Screening	Baseline ^b	Cycle 1				Cycle 2 or later				Discontinuation	Last observation visit ^q
Day	-14 to -4	-3 to -1	1	8 (±2)	15 (±2)	22 (±2)	1 ^l (±3)	8 ^m (±3)	15 (±3)	22 ^m (±3)	(+7)	30 days after last administration (+7)
Informed consent ^a	X											
Inclusion/exclusion	X	X										
Demographic	X											
Prior medications and complication	X											
ECOG-PS	X	X					X				X ^o	
Physical examination, Vital signs, SPO ₂ , Height ^b , Weight	X	X		X	X	X	X	X	X	X	X ^o	X
12-lead ECG	X	X			X		X				X ^o	
MUGA or echocardiogram	X										X ^o	
Gastroenterological endoscopy	X ^f											
Laboratory test ^c	X	X		X	X	X	X	X	X	X	X ^o	X
Pregnancy test	X	X									X ^o	
Child-Pugh score	X	X					X				X ^o	
Lenvatinib administration			Throughout									
Lenvatinib PK blood sampling			X ⁱ		X ⁱ		X ⁱ					
Nivolumab administration			X		X		X		X			
Nivolumab PK blood sampling			X ^s		X ⁿ		X ^t		X ^u		X	X
Anti-nivolumab antibodies (ADA) blood samples			X ⁿ		X ⁿ		X ^v				X	X
Lenvatinib PD biomarker blood sampling			X ⁿ		X ⁿ		X ⁿ					
Nivolumab PD biomarker blood sampling			X ^w				X ^w				X ^w	
Archival tissues ^d							X					
Biopsy ^e	X											
CT assessment/Tumor marker	X ^g						X ^j				X ^p	
Hospitalization				X ^k								
Survival												X ^r
Adverse event			Throughout									

Table 9 Schedule of Procedures/Assessments in Study E7080-J081-117 (for Part 1 and Part 2)

Concomitant medications/therapies	Throughout

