5.6.4 Laboratory Values

Laboratory results will be summarized using Système International (SI) units. For all quantitative parameters, the actual value and the change from baseline to each postbaseline visit will be summarized by visit using summary statistics. Qualitative parameters will be summarized by number and percentage of subjects, and changes from baseline to each postbaseline visit will be reported using shift tables. Percentages will be based on the number of subjects with both nonmissing baseline and relevant postbaseline results.

Box plot display will be used to show the longitudinal change of the parameters by visit.

Laboratory test results will be assigned a low/normal/high (LNH) classification according to whether the value is below (L), within (N), or above (H) the laboratory parameter's reference range. The result of LNH classification will be provided in a subject data listing.

Laboratory parameters will be graded by CTCAE ver. 4.03 in the [section 13](#). Changes from CTCAE grade at baseline to each postbaseline visit and worst postbaseline will be reported using shift tables. CTCAE will also be used to identify subjects with Treatment-emergent markedly abnormal laboratory value (TEMAV). The number (percentage) of subjects with TEMA (markedly abnormal high/low) will be summarized for each visit and overall study period. The TEMA will be defined in the [section 8.3](#).

Subject data listings will be provided.

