8.1 General Data Handling

Definition of Baseline data

Baseline is defined as the last non-missing value observed prior to the first dose of study treatment for a given parameter.

Definition of Change from Baseline, Percent Change from Baseline

Change from baseline is defined as post-baseline value minus baseline value.

Percent change from baseline is defined as follows:

$$\% \text{ Change from baseline} = (\text{Change from baseline} / \text{Baseline}) * 100\%$$

For any Baseline value of 0, the subject's corresponding percent change from baseline will not be included in the summary statistics table.

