Calculation of creatinine clearance

To calculate a creatinine clearance (mL/min), the Cockcroft & Cault formula will be used.

Males: $((140 - \text{age (years)}) \times \text{weight (kg)}) / (\text{Creatinine (serum:mg/dL}) \times 72)$

Females: $((140 - \text{age (years)}) \times \text{weight (kg)} \times 0.85) / (\text{Creatinine (serum:mg/dL}) \times 72)$

Visit Windows

The purpose of visit windows is to provide a single record per subject per visit for the calculation of descriptive statistics for safety parameters (e.g., laboratory values and vital signs, etc.) per scheduled visit, and change from baseline per visit. Other safety analyses (e.g., worst grade laboratory results) will include all observations.

The observation closest to the target date will be used in by visit summaries. If two or more observations have the same distance to the target visit day, the one that has the highest CTCAE grade or is furthest away from the normal range will be used for summary tables. If

the multiple data in the same distance to the target date are in the same range from normal value, the data measured at an earlier date will be used for summary tables.

The visit window is applied for safety assessment item which is scheduled at each visit.

Analysis visit	Target Day	Visit Window	
		Start Day of Visit Window	End Day of Visit Window
Cycle 1 Day 8	Cycle 1 Day 1 + 7	Cycle 1 Day 1 + 5	Cycle 1 Day 1 + 9
Cycle 1 Day 15	Cycle 1 Day 1 + 14	Cycle 1 Day 1 + 12	Cycle 1 Day 1 + 16
Cycle 1 Day 22	Cycle 1 Day 1 + 21	Cycle 1 Day 1 + 19	Cycle 1 Day 1 + 23
Cycle 2 Day 1	Cycle 1 Day 1 + 28	Cycle 1 Day 1 + 28	Cycle 1 Day 1 + 31
Cycle 2 Day 8	Cycle 1 Day 1 + 35	Cycle 1 Day 1 + 32	Cycle 1 Day 1 + 38
Cycle 2 Day 15	Cycle 1 Day 1 + 42	Cycle 1 Day 1 + 39	Cycle 1 Day 1 + 45
Cycle 2 Day 22	Cycle 1 Day 1 + 49	Cycle 1 Day 1 + 46	Cycle 1 Day 1 + 52
Cycle n Day 1 ($n \geq 3$)	Cycle 1 Day 1 + 28 x (n-1)	Cycle 1 Day 1 + 28 x (n-1) - 3	Cycle 1 Day 1 + 28 x (n-1) + 3
Cycle n Day 8 ($n \geq 3$)	Cycle 1 Day 1 + 28 x (n-1) + 7	Cycle 1 Day 1 + 28 x (n-1) + 4	Cycle 1 Day 1 + 28 x (n-1) + 10
Cycle n Day 15 ($n \geq 3$)	Cycle 1 Day 1 + 28 x (n-1) + 14	Cycle 1 Day 1 + 28 x (n-1) + 11	Cycle 1 Day 1 + 28 x (n-1) + 17
Cycle n Day 22 ($n \geq 3$)	Cycle 1 Day 1 + 28 x (n-1) + 21	Cycle 1 Day 1 + 28 x (n-1) + 18	Cycle 1 Day 1 + 28 x (n-1) + 24
End of Treatment	30 days after last dose	Date of last dose	Date of last dose + 37

C1D1 is the day of first dosing.

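### The creatinine shift tables grade baseline on ULN alone but later values on ULN or the subject's own baseline, so most Grade 0 to Grade 1 shifts would be noise

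*SAP*

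**What the plan says.** SAP 5.6.4 states: "Laboratory parameters will be graded by CTCAE ver. 4.03", referring to the table in SAP 13. Its outputs include grade shifts: "Changes from CTCAE grade at baseline to each postbaseline visit and worst postbaseline will be reported using shift tables".

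In SAP 13.1 the Grade 1 cell for creatinine (high) reads ">1 - 1.5 x baseline; >ULN - 1.5 x ULN". The semicolon is not defined, and no footnote limits the baseline limb to values above ULN. Grades 2 and 3 also carry a baseline limb and a ULN limb; Grade 4 has a ULN limb only. Hemoglobin (high) in the same table brings in the subject's baseline conditionally: "or above baseline if baseline is above ULN". Both SAP versions in the file print the same creatinine row.

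Two data-handling rules matter. SAP 8.1: "Baseline is defined as the last non-missing value observed prior to the first dose of study treatment for a given parameter". SAP 8.3, on visit windows: "Other safety analyses (e.g., worst grade laboratory results) will include all observations".

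**The concern.** A shift table is readable only if its two margins use the same scale. Here they do not. The ratio of baseline to itself is exactly 1.0, so the baseline limb can never grade a baseline value, but it can grade every later one. A subject moving from 0.80 to 0.81 mg/dL, both normal on an ordinary reference range, is tabulated as worsening from Grade 0 to Grade 1. Taking the worst of all observations against a single baseline makes such a rise likely by chance.

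Laboratory tests are among the primary safety endpoints. The study has a single arm, so no control column shows how often this happens without drug. The protocol also treats renal events as relevant, with renal in the list of managed adverse event groups (9.4.1.6) and separate proteinuria rules (9.4.1.5). A reader of the worst-grade table could see most subjects worsening on creatinine and take it for a drug effect.

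**Working it through.** The plan states no figure for this row, so there is none to reproduce.

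**Inputs from the documents**
- Creatinine is a scheduled test: "Blood urea nitrogen, creatinine" in protocol Table 8.
- Protocol Table 9 (row "Laboratory test") places postbaseline samples on Days 8, 15 and 22 of Cycle 1, and on Days 1, 8, 15 and 22 of each later cycle.
- Table 9 footnote m allows Day 8 and Day 22 items to be omitted from Cycle 3 onward.
- Scheduled values per subject (k) are therefore 3 after Cycle 1 and 3 + 4 = 7 through Cycle 2. Through Cycle 4, k runs from 7 + 2×2 = 11 to 7 + 2×4 = 15. Discontinuation and last-observation visits can add up to two more.
- Inclusion criterion 8 admits creatinine above ULN, so some subjects may start at Grade 1 or higher.

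**Reading of the semicolon.** I take it as *or*. If both limbs were required, no baseline value could ever be graded, yet the shift tables and the SAP 8.3 definition of markedly abnormal values (TEMAV) need a baseline grade.

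**Exact result, subject starting at or below ULN.** With no renal effect, baseline and the k later values are exchangeable. Baseline is the largest of k + 1 values with probability 1/(k+1). Ignoring ties, P(worst value > baseline) = k/(k+1):

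| Data through | k | k/(k+1) |
|---|---|---|
| one visit | 1 | 50% |
| Cycle 1 | 3 | 75% |
| Cycle 2 | 7 | 87.5% |
| Cycle 4, items omitted | 11 | 91.7% |
| Cycle 4, all items | 15 | 93.75% |

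**Simulation, no renal effect, 400,000 subjects per setting.** Assumptions not in the documents: within-subject CV 3–10%, results rounded to 0.01 mg/dL, ULN 1.07 mg/dL, and 5–25% of subjects with true creatinine above ULN. Entries are the share whose worst postbaseline grade exceeds the baseline grade:

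| Rule and subjects | k = 7 | k = 15 |
|---|---|---|
| Printed row, baseline at or below ULN, CV 3–10% | 83–90% | 91–96% |
| Printed row, all subjects, CV 3–10% | 64–82% | 70–88% |
| Printed row, all subjects, CV 5% | 66.2–81.1% | 71.5–87.8% |
| ULN limb only, all subjects, CV 5% | 4.0–11.5% | 5.4–14.7% |
| ULN limb only, all subjects, CV 3–10% | 2.2–24.2% | 2.8–31.4% |

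For 20 Part 2 subjects at k = 7 and CV 5%, the printed row gives 20 × 0.662 = 13.2 to 20 × 0.811 = 16.2 expected shifts. The ULN limb gives 20 × 0.040 = 0.8 to 20 × 0.115 = 2.3.

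Most of these shifts occur with every value normal. At k = 15 and CV 5%, with 5% of subjects above ULN, 82.4% of all subjects shift without any postbaseline value above ULN, out of 87.8% who shift at all.

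**Higher grades.** A separate simulation at CV 4–6% put no worst value above 1.5 × baseline, so noise does not reach Grade 2 through the baseline limb. No run at CV 3–10% produced Grade 3 or higher.

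**The case against.** The strongest reply is that the plan does what it should. Protocol 9.7.1.8.3 requires CTCAE v4.03 grades by visit and maximum postbaseline grades, and SAP 13.1 presents the row as v4.03. Replacing the Grade 1 cell would depart from the protocol. This stands. The published criteria were not available here, so nothing is claimed about whether the row is a faithful copy. A faithful copy would produce the same asymmetry in a baseline-to-worst shift table.

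A second reply is that little depends on these cells. This also stands. Tolerability rests on DLTs and TEMAV needs Grade 3 or higher. A laboratory value becomes an adverse event through intervention, a change in study drug or investigator judgment, not through a derived Grade 1. No statistical comparison is planned.

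A third is that derivation rules and table shells sit in separate documents (SAP 9 and 11) and might already deal with this. They might, but the SAP text does not say so.

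Two stronger readings are tempting. A reader might infer that nearly every subject would show a shift. The documents do not support that for the whole study: subjects admitted above ULN do not shift on small rises, one cycle of data gives 75% rather than 95%, and k = 15 is the most that scheduled visits through Cycle 4 can supply. A reader might also infer that a mild renal effect could not be detected at all. SAP 5.6.4 plans by-visit values, changes from baseline and box plots for quantitative parameters, and these would still show one.

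**Conclusion.** The concern holds for the creatinine grade shift tables, by visit and for the worst value, and within them for the split between Grade 0 and Grade 1. The rule, rather than any drug effect, would produce most of the shifts out of Grade 0.

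The mechanism follows from the SAP text, given that the semicolon means *or*. The k/(k+1) figures need only exchangeable values, no ties and a baseline at or below ULN. The all-subject ranges depend also on the assumed CV, ULN, rounding and share above ULN; the assumed share drives most of the spread. All of them presume that subjects stay on treatment long enough to supply k values.

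Grade 3 or higher, TEMAV, adverse event reporting, DLTs and the ungraded creatinine summaries are unaffected. This is a reporting improvement worth making, not a threat to the study's conclusions.

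**What to change.** Keep the printed creatinine row. Add to SAP 5.6.4 and 13.1 a second creatinine shift row in which baseline and postbaseline values are both graded on the table's ULN limits only, at every grade: above ULN to 1.5, above 1.5 to 3.0, above 3.0 to 6.0, and above 6.0 × ULN. Both margins are then on one scale.

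Add a footnote to the printed row saying that either limb is sufficient and that Grade 1 therefore includes rises over baseline within the normal range.

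Changing only the Grade 1 cell to ULN while keeping the baseline multiples from Grade 2 up would be worse. It departs from the v4.03 row and leaves the two margins on different scales from Grade 2. It also opens a gap: with baseline 0.50 mg/dL and an assumed ULN of 1.07, 0.75 would be Grade 0 and 0.76 Grade 2.

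The cost is one extra derivation, one table row and one footnote. No data collection or clinical rule changes.
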